1 SYNOPSIS

Title: A Phase 4 Multicenter, Randomized, Double-Blind Study of Risankizumab for the Treatment of Adult Subjects with Moderate to Severe Genital Psoriasis or Moderate to Severe Scalp Psoriasis	
Background and Rationale:	
Risankizumab is a humanized mAb of the immunoglobulin (Ig) G1 subclass directed towards IL-23p19. The antibody has been engineered to reduce Fcγ receptor and complement-binding and potential charge heterogeneity. Risankizumab binds with high affinity to human IL-23.
 
Risankizumab is currently approved for marketing in the United States (US), the European Union (EU), Japan, and other countries for the treatment of moderate to severe plaque psoriasis, active psoriatic arthritis, and moderately to severely active Crohn's disease.
 
Risankizumab is also being developed for the treatment of ulcerative colitis.
 
This study is designed to evaluate the treatment effect of risankizumab in moderate to severe genital psoriasis and moderate to severe scalp psoriasis.

Objective(s) and Endpoint(s):	
The primary objective of the study is to evaluate the efficacy and safety of risankizumab for the treatment of moderate to severe genital psoriasis (Study-G) or moderate to severe scalp psoriasis (Study-S) in adults who are candidates for systemic therapy.
 
The primary endpoints are:
 
 • Study-G: Achievement of static Physician Global Assessment of Genitalia (sPGA-G) of 0 or 1 at Week 16 • Study-S: Achievement of scalp Investigator Global Assessment (IGA) of 0 or 1 at Week 16 
Ranked secondary endpoints are:
 
Study-G
 
 1. Achievement of sPGA-G of 0 at Week 16 2. Achievement of Dermatology Life Quality Index (DLQI) of 0 or 1 at Week 16 3. Achievement of clinically meaningful (≥ 4-point) improvement from baseline on the Genital Psoriasis Itch Numerical rating scale (NRS) at Week 16 among subjects with baseline scores ≥ 4 4. Achievement of Genital Psoriasis Sexual Frequency Questionnaire (GenPs-SFQ) item 2 score of 0 or 1 at Week 16 among subjects with baseline scores ≥ 2 
Study-S
 
 1. Achievement of ≥ 90% improvement from baseline in Psoriasis Scalp Severity Index (PSSI) 90 at Week 16 2. Achievement of PSSI 75 (≥ 75% improvement from baseline in PSSI) response at Week 16 3. Change from baseline in Psoriasis Symptom Scale (PSS) at Week 16

	
4. Achievement of PSSI 100 (100% improvement from baseline in PSSI) response at Week 16
 
5. Achievement of PSS of 0 at Week 16

Investigator(s):	Multicenter.
Study Site(s):	45 sites in France, Germany, Italy, Poland, Spain, and United States
Study Population and Number of Subjects to be Enrolled:	The study is designed to randomize approximately 200 adult subjects (100 in Study-G and 100 in Study-S). Subjects must have a current diagnosis of moderate to severe genital psoriasis (Study-G) defined as sPGA-G \geq 3 or moderate to severe scalp psoriasis (Study-S) defined as PSSI \geq 12, scalp IGA \geq 3, and \geq 30% of the scalp affected.
Investigational Plan:	
This is a Phase 4, international, multicenter, randomized, double-blind, placebo-controlled study in subjects with moderate to severe genital psoriasis (Study-G) or moderate to severe scalp psoriasis (Study-S). Each study comprises a 30-day Screening Period, a 16-week double-blind placebo-controlled treatment period (Period A), a 36-week open-label treatment period (Period B), and an 8-week Follow-up Period with a follow-up phone call 20 weeks after last dose of study drug.
 
Eligible subjects within each study will be randomized to receive risankizumab or placebo in a 1:1 ratio. Participants will receive double-blind risankizumab (for those randomized to risankizumab) or matching placebo (for those randomized to placebo) during Period A; all subjects will receive open-label risankizumab during Period B.
 
The primary analysis will be performed after all ongoing subjects have completed Week 16 of Study-G and Study-S and all data pertaining to Period A are cleaned. This will be the only and final analysis for efficacy in Period A for each study, respectively. The final analysis will be conducted upon study completion.

Key Eligibility Criteria:	
Subjects must be at least 18 years old (and also meet the legal age of majority per local law) with a clinical diagnosis of chronic plaque psoriasis with or without psoriatic arthritis for at least 6 months before the Baseline Visit.
 
Subjects must have a current diagnosis of moderate to severe genital psoriasis (Study-G) defined as sPGA-G \geq 3 or moderate to severe scalp psoriasis (Study-S) defined as PSSI \geq 12, scalp IGA \geq 3, and \geq 30% of the scalp affected.
 
Subjects must have body surface area (BSA) \geq 1% with at least 60% of subjects having BSA \geq 10%; sPGA \geq 3; inadequate control of psoriasis and/or intolerance to topical treatment, phototherapy and/or systemic therapy; and be candidates for systemic therapy or phototherapy as assessed by the investigator.

Study Drug and Duration of Treatment:	Study drug will be provided as a solution for injection SC: risankizumab 150 mg/1 mL in pre-filled syringe and matching placebo. Participants will receive a single injection SC of risankizumab (150 mg total dose for those randomized to risankizumab) or matching placebo (for those randomized to placebo), at Baseline/Day 1 and Week 4. Subjects will receive 1 injection SC of risankizumab (150 mg total dosage) at Weeks 16, 28, and 40.
Date of Protocol Synopsis:	07 June 2023

2 INTRODUCTION

2.1 Background and Rationale

Why Is This Study Being Conducted?

Psoriasis is a chronic debilitating immune-mediated disease characterized by marked inflammation of the skin that results in thick, erythematous, scaly plaques involving the skin. In most developed countries, prevalence is between 1.5 and 5%.¹ Twenty-five percent of patients have moderate to severe disease with a considerable negative impact on psychosocial and economic status.² Psoriasis is more than a superficial disease, with up to 30% of patients having joint involvement and a high correlation between psoriasis and obesity, diabetes, depression, metabolic syndrome, and cardiovascular disease.³ Topical therapies are used for limited disease or as an adjunct to systemic therapy or phototherapy for moderate to severe psoriasis.⁴ For more widespread disease, phototherapy is a consideration. Systemic therapies, including methotrexate, cyclosporine⁵, synthetic retinoids⁶, apremilast⁷, and fumaric acid esters can also be used in patients with moderate or severe disease, though known side effect profiles may limit their use.^{8,9}

Biologics have emerged as a preferred alternative treatment option for patients with psoriasis and are now routinely used when traditional systemic agents fail, are not tolerated, or are contraindicated due to comorbid conditions.⁴ These biologic agents include TNF-alpha inhibitors (etanercept^{10,11}, infliximab^{12,13}, certolizumab pegol^{14,15}, and adalimumab^{16,17}), the IL-12/23 inhibitor (ustekinumab^{18,19}), IL-17A inhibitors (secukinumab^{20,21}, brodalumab^{22,23}, and ixekizumab^{24,25}), and IL-23p19 inhibitors (guselkumab^{26,27}, tildrakizumab^{28,29}, and risankizumab^{30,31}).

IL-23 plays a critical role in the differentiation and function of Th17 cells, which are an important T-cell subpopulation involved in the pathogenesis of immune mediated disorders.³²

There is still clinical need for increased efficacy as the most effective anti-TNF and anti-IL-12/23 agents provide approximately 75% improvement in psoriasis in about 50 to 80% of patients and these responses can be lost over time. While the anti-IL-17A, -IL-17RA, and -IL-23p19 agents (i.e., secukinumab, ixekizumab, brodalumab and guselkumab) may provide better efficacy than anti-TNF therapies and ustekinumab, they require monthly or every other month injections.³³⁻³⁶ Studies show patients prefer less frequent dosing intervals for biologics in psoriasis management.³⁷

Psoriasis often manifests in areas that are difficult to treat, such as the genitals (14% – 43%) and scalp (43% – 65%).³⁸⁻⁴³ Scalp psoriasis is characterized by demarcated erythematous squamous chronic plaques that often advance beyond the hairline into the face and retroauricular region. Due to its visibility, scaling of the scalp negatively impacts quality of life, often causing embarrassment and psychosocial handicap. Topical treatments are less effective on the scalp than other body areas because the scalp is relatively inaccessible and hair making adherence and the use of ointments and cream-based products challenging, often leading to poor compliance.⁴⁴

Genital psoriasis frequently remains undiagnosed in patients due to insufficient evaluation of genital involvement and a reluctance of patients and healthcare providers to discuss genital psoriasis.⁴⁵ Psoriasis affecting genital areas may be associated with considerable morbidity, discomfort and embarrassment and may significantly impair the quality of life and psychosexual wellbeing of

patients.⁴⁶ Many standard topical or ultraviolet-based treatments for psoriasis are either contraindicated or not well tolerated on sensitive genital skin, limiting treatment options. Systemic therapies are indicated by current treatment guidelines for areas that are difficult to treat such as genital psoriasis or scalp psoriasis, even in patients with lower BSA involvement.⁴⁷

Risankizumab is currently approved for marketing in the US, the EU, Japan, and other countries for the treatment of moderate to severe plaque psoriasis, active psoriatic arthritis, and moderately to severely active Crohn's disease. Risankizumab is also being developed for the treatment of ulcerative colitis.

Risankizumab is a humanized mAb of the Ig G1 subclass directed towards IL-23p19. The antibody has been engineered to reduce Fcγ receptor and complement binding and potential charge heterogeneity. Risankizumab binds with high affinity to human IL-23.

The risankizumab clinical program assessed the efficacy and safety versus placebo and other commonly used biological therapies such as adalimumab, ustekinumab, and secukinumab up to 1 year. Risankizumab showed high levels of sustained clearance in these clinical trials and demonstrated superior efficacy relative to comparators at the assessed primary endpoints.

2.2 Benefits and Risks to Subjects

Risankizumab is a humanized Ig G1 mAb directed against the p19 subunit of the human cytokine IL-23. IL-23 is implicated in the pathophysiology of immune-mediated inflammatory diseases.

The Phase 3 pivotal program with risankizumab demonstrated efficacy for improvement in signs and symptoms of plaque psoriasis and the safety results were consistent with those known to be associated with mechanism of action or other appropriate safety findings. Taken together, the safety and efficacy data from the Phase 3 program support further development of risankizumab in subjects with psoriasis.

This study is designed to evaluate the treatment effect of risankizumab in moderate to severe genital psoriasis and moderate to severe scalp psoriasis.

As with any immune modulating agent, risankizumab may impair immune function resulting in a risk of infection. This will be monitored by collection of all AEs during the treatment and observation periods. In addition, subjects with clinically important active infection will not be included in the study. The safety profile in the global pivotal trials was consistent with that observed in Phase 2 clinical trials, with no important identified risks for risankizumab through 4.5 years of continuous risankizumab treatment in an ongoing open-label extension study.

Subjects with a positive QuantiFERON[®]-TB (or IGRA equivalent)/TB skin test result must fulfill entry criteria as specified in Section 5.1 of this protocol. IL-23 inhibition is not known to increase the risk of TB infection or impair the response to TB infection in animal models.^{48,49} Subjects with positive QuantiFERON-TB testing (or IGRA equivalent)/TB skin test who have latent TB (defined by local guidelines) should be treated as per local guidelines or by investigator judgement with TB prophylaxis prior to receiving risankizumab and should be carefully monitored for any sign of TB reactivation.

Published literature indicates that inhibition of IL-23 is unlikely to increase the risk for cancer. Expression of IL-23 is increased in human tumors.⁵⁰⁻⁵² Moreover, preclinical data have demonstrated a beneficial effect of IL-23 p19 inhibition in animal models, both for pre-existing and tumor-induction models.⁵³

While there is not enough clinical information at this time to rule out a risk of cancer with risankizumab, this risk is considered small.

Although rare, a potential for hepatic AEs is under constant surveillance by sponsors and regulators. Therefore, this study is designed to enable timely detection, evaluation, and follow-up of laboratory alterations in selected liver laboratory parameters to ensure subjects' safety.

Increases in MACE, including myocardial infarction, cerebrovascular accident, and cardiovascular death, reported initially with anti-IL-12/23 agents such as ustekinumab have not been observed in longer-term studies with risankizumab. While the likelihood of increased MACE is small, all suspected cardiovascular or cerebrovascular events (serious or nonserious) observed in this study will be adjudicated by an independent CAC. The committee will remain blinded to treatment allocation (Section 6.2).

Local reactions to subcutaneously administered biologic therapies are usually limited to redness, swelling, or induration at the injection site. Manifestations of systemic hypersensitivity reactions may include anaphylaxis, generalized urticaria, hypotension, and respiratory distress. Both local and systemic hypersensitivity reactions are typically readily detectable, transient in nature, and manageable with standard medical treatment. Subjects will be closely monitored during study drug administration. An independent AAC will adjudicate observed systemic hypersensitivity and anaphylactic events. The AAC will remain blinded to treatment allocation (Section 6.3).

There are no important identified risks for risankizumab.⁵⁴

In conclusion, the benefit-risk profile of risankizumab is considered appropriate for this stage of clinical development.⁵⁵ Based on data from the integrated safety analyses, risankizumab is safe and well-tolerated and demonstrates a favorable benefit-risk profile.

For further details, please see findings from completed studies, including safety data in the risankizumab Investigator Brochure.⁵⁴

In view of the COVID-19 pandemic, the benefit-risk profile of various immunomodulatory therapies on COVID-19 is being evaluated based on real world and clinical trial data. At this time, the effects of risankizumab on the course of COVID-19 are not well defined.

3 OBJECTIVES AND ENDPOINTS

3.1 Objectives, Hypotheses, and Estimands

The primary objective of the study is to evaluate the efficacy and safety of risankizumab for the treatment of moderate to severe genital psoriasis (Study-G) or moderate to severe scalp psoriasis (Study-S) in adults who are candidates for systemic therapy.

Hypotheses and Estimand for the Primary Objective

The primary endpoints are achievement of static sPGA-G of 0 or 1 at Week 16 for subjects in Study-G, and achievement of scalp IGA of 0 or 1 at Week 16 for subjects in Study-S.

The hypotheses corresponding to the primary efficacy objective are:

- The proportion of subjects achieving sPGA-G of 0 or 1 at Week 16 in subjects treated with risankizumab is greater than those treated with placebo in Study-G.
- The proportion of subjects achieving scalp IGA of 0 or 1 at Week 16 in subjects treated with risankizumab is greater than those treated with placebo in Study-S.

The estimand corresponding to the primary endpoints in Study-G and Study-S are defined as follows:

- Study-G: Difference in the proportion of subjects achieving sPGA-G of 0 or 1 at Week 16, regardless of premature discontinuation of study drug, in the risankizumab group compared with the placebo group among adult subjects with moderate to severe genital psoriasis who are candidates for systemic therapy.
- Study-S: Difference in the proportion of subjects achieving scalp IGA of 0 or 1 at Week 16, regardless of premature discontinuation of study drug, in the risankizumab group in compared with the placebo group among adult subjects with moderate to severe scalp psoriasis who are candidates for systemic therapy.

Intercurrent events handling: No intercurrent event is considered.

The ranked secondary endpoints are as defined in Section 3.3.

The estimands corresponding to these ranked secondary endpoints are:

- Binary endpoints: The estimand is defined as the difference in the proportion of subjects achieving each endpoint, regardless of premature discontinuation of study drug, in the risankizumab group versus the placebo group in subjects with moderate to severe genital psoriasis in Study-G or in subjects with moderate to severe scalp psoriasis in Study-S.
- Continuous endpoint (change from Baseline in PSS for Study-S): The estimand is defined as the difference in mean change from Baseline in PSS at Week 16, regardless of premature discontinuation of study drug, in the risankizumab group versus the placebo group in subjects with moderate to severe scalp psoriasis in Study-S.

Intercurrent events handling: No intercurrent event is considered.

3.2 Primary Endpoints

The primary endpoints are:

- Study-G: Achievement of sPGA-G of 0 or 1 at Week 16
- Study-S: Achievement of scalp IGA of 0 or 1 at Week 16

3.3 Secondary Endpoint

Ranked Secondary Endpoints

Study-G

1. Achievement of sPGA-G of 0 at Week 16
2. Achievement of DLQI of 0 or 1 at Week 16
3. Achievement of clinically meaningful (≥ 4 -point) improvement from baseline on the Genital Psoriasis Itch NRS at Week 16 among subjects with a baseline score ≥ 4
4. Achievement of GenPs-SFQ item 2 score of 0 or 1 at Week 16 among subjects with a baseline score ≥ 2

Study-S

1. Achievement of $\geq 90\%$ improvement from baseline in PSSI 90 at Week 16
2. Achievement of PSSI 75 ($\geq 75\%$ improvement from baseline in PSSI) response at Week 16
3. Change from baseline in PSS at Week 16
4. Achievement of PSSI 100 (100% improvement from baseline in PSSI) response at Week 16
5. Achievement of PSS of 0 at Week 16

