7.4 Statistical Analyses for Efficacy

Summary and Analysis of the Primary Endpoint

Analysis of the primary endpoint will be conducted on the ITT_G and ITT_S Populations for Study-G and Study-S, respectively, based on treatment as randomized.

Comparison of the primary endpoint will be made between risankizumab and placebo using the CMH test adjusting for the actual values of stratification factors weight (≤ 100 kg vs. > 100 kg) and number of prior biologic therapies for psoriasis (0 vs. ≥ 1), with a 2-sided significance level of 0.05 for each study.

Handling of Missing Data

- Non-responder Imputation (NRI) will be the primary approach to handle missing values. In cases data missing at random can be reasonably assumed, NRI while incorporating multiple imputation to handle any missing data that can be reasonably assumed to be Missing at Random (NRI-MI) will be used.

Details for NRI, NRI-MI, and other sensitivity analysis (if applicable) will be provided in the SAP.

Summary and Analysis of Ranked Secondary Endpoints

Analysis of all ranked secondary efficacy endpoints will be conducted on the ITT_G and ITT_S Populations based on treatment as randomized respectively in each study.

The categorical endpoints will be analyzed using the CMH test described above.

The continuous endpoints will be analyzed using a MMRM, including baseline, adjusting for treatment, actual values of stratification factors, visit, and treatment by visit interaction.

Summary and Analysis of Additional Efficacy Endpoints

Details for the analyses of additional efficacy endpoints will be provided in the SAP.

Subgroup Analysis for Efficacy

To evaluate the consistency of the efficacy across demographic and other baseline characteristics, the number and percentage of subjects achieving sPGA-G of 0 or 1 at Week 16 (for ITT_G Population) and scalp IGA of 0 or 1 at Week 16 (for ITT_S Population) will be summarized among the following subgroups:

- BMI (normal: < 25; overweight: ≥ 25 to < 30; obese: ≥ 30)
- BSA (< 10%, ≥ 10%)
- Prior biologic therapies for psoriasis (0, ≥ 1)
- Weight (≤ 100 kg, > 100 kg)
- Baseline sPGA (3,4)
- Baseline sPGA-G (3,4) for Study-G only
- Baseline scalp IGA (3,4) for Study-S only
- Baseline PSSI (by median) for Study-S only

The BMI ≥ 30 subgroups will be combined with the adjacent subgroup when having fewer than 10% subjects.

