9.0 Efficacy Analyses

9.1 General Considerations

All efficacy analyses will be conducted on the ITT Population separately for each study.

The primary analysis will be performed when all ongoing subjects complete Week 16 of Study-G and Study-S and all data pertaining to Period A are cleaned. The Week 16 analysis is the only and final analysis for efficacy in Period A.

The final analysis will be conducted upon study completion.

For categorical variables, the number and proportion of subjects, and the 95% confidence interval (CI) of the proportion will be provided by each treatment group among ITT Populations.

In addition, comparisons between RZB and placebo will be analyzed using the Cochran-Mantel-Haenszel (CMH) test adjusting for the actual values of stratification factors weight (≤ 100 kg, > 100 kg) and number of prior biologic therapies for psoriasis ($0, \geq 1$), with a 2-sided significance level of 0.05 for each study. The CMH test will use weights proposed by Greenland & Robins, which is calculated as follows:

$$\hat{\delta}_{MH} = \frac{\sum_{i=1}^4 w_i \hat{\delta}_i}{\sum_{i=1}^4 w_i}, \text{ where}$$

- $\hat{\delta}_i = \frac{x_i}{n_i} - \frac{y_i}{m_i}$ denotes the risk difference in stratum $i, i = 1, \dots, 4$.
- $w_i = \frac{n_i m_i}{n_i + m_i}$ denotes the weight of stratum $i, i = 1, \dots, 4$.
- x_i denotes the number of subjects with event in RZB in stratum $i, i = 1, \dots, 4$.
- y_i denotes the number of subjects with event in PBO in stratum $i, i = 1, \dots, 4$.
- n_i denotes the number of subjects in RZB in stratum $i, i = 1, \dots, 4$.
- m_i denotes the number of subjects in PBO in stratum $i, i = 1, \dots, 4$.

The estimated variance of $\hat{\delta}_{MH}$ is calculated as:

$$\widehat{var}(\hat{\delta}_{MH}) = \frac{\sum_{i=1}^4 L_i}{(\sum_{i=1}^4 w_i)^2}$$

$$\text{where } L_i = \frac{x_i(n_i - x_i) m_i^3 + y_i(m_i - y_i) n_i^3}{n_i \cdot m_i \cdot (n_i + m_i)^2}, i = 1, \dots, 4$$

Assuming a normal distribution of $\hat{\delta}_{MH}$, an approximate 95% CI is given as follows, where $z_{0.975}$ is the 97.5% quantile of $N(0, 1)$:

$$CI = \left[\hat{\delta}_{MH} \pm z_{0.975} \cdot \sqrt{\widehat{var}(\hat{\delta}_{MH})} \right]$$

The approximate p-value can be calculated using the following:

$$p - \text{value} = 2 \cdot \Pr \left[Z > \left| \frac{\hat{\delta}_{MH}}{\sqrt{\widehat{var}(\hat{\delta}_{MH})}} \right| \right], \text{ where } Z \sim N(0, 1)$$

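### DLQI 0/1 and PSS 0 are ranked as fixed Week 16 thresholds but tested without the subject's own baseline score, which gives up precision if baseline is prognostic

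*Protocol*

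**What the plan says.** Protocol 3.3 lists "Achievement of DLQI of 0 or 1 at Week 16" as Study-G rank 2 and "Achievement of PSS of 0 at Week 16" as Study-S rank 5; SAP 3.2 repeats them for the whole ITT population of each study. Both belong to the fixed testing sequence at two-sided 0.05 (Protocol 7.7, SAP 13.0). The eligibility criteria in Protocol 5.1 set no minimum DLQI or PSS.

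For the ranked binary endpoints, Protocol 7.4 states: "The categorical endpoints will be analyzed using the CMH test described above". That refers to the primary analysis, made "using the CMH test adjusting for the actual values of stratification factors weight" and number of prior biologics. SAP 9.1 gives the same four strata, a Mantel-Haenszel-weighted risk difference, and a Wald p-value from the Greenland-Robins variance. These two factors are also the only ones that stratify treatment allocation.

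For continuous endpoints the plan differs: "The continuous endpoints will be analyzed using a MMRM, including baseline". PSS change, Study-S rank 3, is therefore baseline-adjusted. The multiple-imputation model for the primary endpoints (SAP 9.3.3) also contains the baseline value. Baseline DLQI and PSS are collected (Protocol Appendix D) and summarised (SAP 7.1). SAP 9.4.3 rules out any sensitivity analysis of the ranked secondaries.

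**The concern.** With an absolute threshold, the change a subject needs depends on where that subject starts. On the 0-30 DLQI scale, a subject at 25 must fall by 24 points to reach 1, while a subject who enters at 0 or 1 meets the criterion without any change. PSS 0 behaves the same way. Baseline is therefore a plausible predictor of response, and the planned test ignores it. The plan is also uneven: PSS in the same subjects at the same visit is baseline-adjusted at rank 3 and not at rank 5.

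The stakes are precision, and how far the reported difference moves with a chance baseline imbalance. DLQI 0/1 matters more because it gates the itch and GenPs-SFQ tests; PSS 0 is last in its sequence. The sample-size sections give power only for the primary endpoints, so no power margin is documented for either rank.

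**Working it through.** **Inputs from the documents.** 50 per arm, 1:1 allocation, two-sided alpha 0.05, four strata, and the SAP 9.1 estimator and variance. Primary rates: Study-G 13% versus 13 + 53 = 66%; Study-S 11% versus 11 + 37 = 48%.

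**Assumed, because the documents give none.** DLQI 0/1 and PSS 0 response rates, stratum shares (45/20/25/10%), and the link between baseline and Week 16 response, expressed as a latent-normal correlation rho.

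**Step 1: the plan's own figure.** Power = Φ{[|p1 − p2|√n − 1.96√(2p̄(1 − p̄))] / √(p1(1 − p1) + p2(1 − p2))}.
- Study-G: (0.53 × 7.071 − 1.96 × 0.6913) / 0.5810 = 4.12, power 99.998%.
- Study-S: (0.37 × 7.071 − 1.96 × 0.6449) / 0.5895 = 2.29, power 98.9%.

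Both agree with the stated more than 90%. The same formula at an assumed 10% versus 30% gives (0.20 × 7.071 − 1.96 × 0.5657) / 0.5477 = 0.56, power 71%. A ranked secondary with an effect of that size would not share the primary's margin.

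**Step 2: planned CMH against a baseline-adjusted risk difference.** Simulation of 3000 trials per scenario, 50 per arm. The adjusted estimate is a logistic-standardised risk difference with the baseline score added.

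| Placebo vs active | rho | Variance ratio, adjusted/planned | Power, planned → adjusted |
|---|---|---|---|
| 5% vs 20% | 0.2 | 1.004 | 69.1% → 66.7% |
| 5% vs 20% | 0.4 | 0.954 | 67.1% → 67.2% |
| 5% vs 20% | 0.6 | 0.873 | 68.9% → 74.4% |
| 10% vs 30% | 0.4 | 0.947 | 75.9% → 77.3% |
| 10% vs 30% | 0.6 | 0.819 | 76.2% → 82.8% |
| 10% vs 40% | 0.2 | 0.995 | 95.5% → 95.1% |
| 10% vs 40% | 0.4 | 0.932 | 95.9% → 96.6% |
| 10% vs 40% | 0.6 | 0.835 | 96.1% → 98.5% |
| 20% vs 50% | 0.2 | 0.994 | 91.4% → 90.4% |
| 20% vs 50% | 0.4 | 0.902 | 91.3% → 92.7% |
| 20% vs 50% | 0.6 | 0.810 | 90.7% → 95.1% |

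The mean difference is the same with and without adjustment (0.201 and 0.201 at 10% vs 30%, rho 0.6), so the planned estimate is unbiased.

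**Step 3: like-for-like power at 10% versus 30%, strong link.** The SAP's Wald test rejects at about 6-8% under the null because strata are sparse and counts low, whether or not baseline is prognostic. The logistic-standardised test rejects at about 6%. Planned and adjusted power must therefore be compared with the same type of variance.
- Normal approximation from the simulated SDs: Φ(0.201/0.0786 − 1.96) = Φ(0.60) = 72.5% and Φ(0.201/0.0711 − 1.96) = Φ(0.87) = 80.7%, a gain of about 8 points.
- Null-variance test on both sides, baseline DLQI in five bands, randomization-based ANCOVA: 71.4% to 77.2% in one simulation (variance ratio 0.886) and 72.5% to 76.8% in another (0.89), gains of about 6 and 4 points.

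**Step 4: chance imbalance.** The standard error of the baseline mean difference is √(1/50 + 1/50) = 0.2 SD. At 10% versus 30%, an imbalance of that size moves the planned estimate by 1.9 points (rho 0.4) or 3.3 points (rho 0.6), and the adjusted estimate by about 0. This is the Step 2 loss seen from another side: (0.033/0.0786)² = 0.18, against a variance saving of 1 − 0.819 = 0.18.

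**Step 5: adding baseline as a CMH stratum.** A median split gives eight strata. Null rejection rose to 8-9% (11-12% with 25 per arm), with little or no gain in SD at rho 0.4 or below.

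**The case against.** **The test is valid.** Under randomization the CMH difference is unbiased and its standard error already covers chance imbalance. A reader might infer that subjects who start at the threshold bias the comparison, or that omitting baseline inflates the false-positive rate. Neither follows: such subjects fall in both arms by chance. The 6-8% null rejection comes from the Wald variance in sparse strata and is a separate matter.

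**The gain is conditional.** This stands. No PRO correlation, baseline distribution or response rate is documented, and PSS 0 has not been modelled separately from the generic scenarios.

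**Mixed variance types can erase the gain.** This stands as a caution. Comparing the planned Wald test (76.2%) with a null-variance adjusted test (76.8%) shows almost nothing, because the first is slightly liberal. It does not affect the variance ratios.

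**Baseline-adjusted evidence already exists.** PSS change is rank 3, and DLQI change is an additional Study-G endpoint. That helps interpretation, but it does not sharpen the ranked DLQI 0/1 or PSS 0 test.

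**The same criticism might seem to cover the other ranked patient-reported responder endpoints.** It does not carry over equally. GenPs-SFQ is defined as "Achievement of GenPs-SFQ item 2 score of 0 or 1 at Week 16 among subjects with a baseline score ≥ 2", so nobody analysed starts as a responder and only scores 2 to 4 remain. With an assumed 25 per arm, the variance ratio was 0.99-1.00 at rho 0.2 and about 0.92 at rho 0.4, with no clear power gain. The itch endpoint is a change from baseline, outside this rationale.

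**The method was specified after agency feedback.** The SAP version history says so for version 2.0. That is a fair reason for caution in replacing the confirmatory test, but not for excluding a sensitivity analysis.

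**Conclusion.** The point holds for DLQI 0/1 and PSS 0 as a conditional loss of efficiency. If baseline is moderately to strongly prognostic (rho 0.4 to 0.6), adjustment would lower the variance of the risk difference by about 5-19%. For DLQI 0/1 at an assumed 30% versus 10%, like-for-like power at a strong link is about 4-8 points lower than it could be; at a moderate link the simulated gain is 0 to 1.4 points. At rho 0.2 there is no gain, and adjustment may cost about 0-2 points (2.4 in the worst row of the table).

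These sizes rest on assumed rates, stratum shares and correlations. The text itself is not in doubt: two fixed thresholds without a baseline condition, a test that omits baseline, and a plan that adjusts for it elsewhere. The documents do not support calling the planned test biased, or treating the precision loss as certain.

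**What to change.** Before unblinding, state in SAP 9.1 and 9.4.2 that DLQI 0/1 (Study-G) and PSS 0 (Study-S) are analysed as a risk difference accounting for the same stratification factors, with the baseline score of the same instrument as a covariate. Either randomization-based ANCOVA or logistic standardisation would serve. Do not add baseline as further CMH strata. Keep alpha and rank order, and report the unadjusted CMH as a sensitivity analysis.

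The text should also name the variance used for the p-value, define baseline PSS as the MMRM does, and give a rule for a missing baseline score so that every ITT subject is kept.

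If the agency-reviewed CMH must remain confirmatory, replace the exclusion in SAP 9.4.3 with the adjusted analysis of these two endpoints as a prespecified sensitivity analysis. Extending it to GenPs-SFQ is optional.

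The cost is SAP wording and a short program, with no new data or subjects, plus possible agency discussion if the confirmatory test changes. The SAP is at version 4.0 (18 February 2025), and the documents do not show whether unblinding has occurred. If it has, the adjusted analysis can only be labelled post hoc.
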